## 7. OBJECTIVES AND ENDPOINTS

The principal objective of the POLYMAILLE® C study is to describe safety and performance of POLYMAILLE® C.

Identification and analysis of potential emergent risks will be performed according to the availability of the collected adverse events.

Identification of possible systematic misuse or off-label use of POLYMAILLE® C, with a view to verifying that the intended purpose is correct, will also be performed according to the availability of the data.

The following table summarizes the performance and safety endpoints and timeframe after surgery.

		Time period following surgery				
Study endpoints		At surgery	30 days	6 months	1 year	>1 year until 5 years of follow-up
		Performance endpoints				
Primary patency rate*	---	X	X	X*	X	
Primary assisted patency rate	---	X	X	X	X	
Secondary patency rate	---	X	X	X	X	
Device Failure	X	X	X	X	X	
Procedural success rate	X	---	---	---	---	
		Safety endpoints				
Mortality rate*	X	X*	X	X	X	
Limb salvage rate	---	X	X	X	X	
Adverse events **	X	X	X	X	X	

---

**PROTOCOL** 2020-PMC-01  
**TITLE:** Safety and Performance of POLYMAILLE® C vascular prosthesis  
**EFFECTIVE DATE:** 15 January 2021

---

*\* Primary endpoint*

*\*\*Listed in section 6.2*

---

PROTOCOL	2020-PMC-01
TITLE:	Safety and Performance of POLYMAILLE® C vascular prosthesis
EFFECTIVE DATE:	15 January 2021

---

## 7.1. Performance endpoints

- Primary performance endpoint is **primary patency rate at 1 year** after surgery using POLYMAILLE® C.
- The others performance endpoints are:
  - **Procedural success rate**, *defined as:*
    - *Ability to use with no need for replacement by another device and,*
    - *Effective vascular flow restoration after procedure and,*
    - *In case of aneurysm, exclusion of aneurysmal portion after procedure.*
  - **Primary patency rate**, *defined as rate of patent grafts without any procedure or intervention of the conduit itself*
  - **Primary assisted patency rate**, *defined as rate of patent grafts, with or without procedure or intervention of the conduit itself after device implantation, such as endovascular balloon angioplasty or anastomotic revision, however with graft never thrombosed (graft occlusion)*
  - **Secondary patency rate**, *defined as rate of patent grafts, with or without procedure or intervention of the conduit itself after device implantation, such as endovascular balloon angioplasty or anastomotic revision, lysis and/or thrombectomy.*
  - **Device Failure**, *defined as:*
    - *Uncontrolled blood leakage from device*
    - *Loss of structural integrity, e.g. rupture and/or exaggerated dilation (> 50 %)*
    - *Occlusion of the device*
    - *Total or partial replacement of the device required*

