## 2. SYNOPSIS

Title:	A Retrospective, Observational, Multicentre Study to Collect Clinical Safety and Performance data on POLYMAILLE® C vascular prosthesis
Study Population:	Subjects who did receive POLYMAILLE® C at least one year ago for replacement or bypass of arteries. 2 main sub-populations will be studied depending on location of surgery (abdominal and peripheral), but data will be collected for all subjects who did receive POLYMAILLE® C.
Study Design:	Multi-center retrospective case series
Study Type:	PMCF
Number of subjects:	Data from a minimum of 200 subjects will be evaluated. A minimum of 100 subjects will be evaluated for each main location of surgery (abdominal and peripheral).
Follow-up	At least 1 year follow-up after surgery until a maximum of 5 years.
Study Product:	POLYMAILLE® C vascular prosthesis
Intended use:	POLYMAILLE® C vascular prostheses are indicated for replacement or bypass of arteries presenting aneurysm or obliterative arterial disease. Their indication is restricted to abdominal and peripheral surgery not crossing the knee flexion crease.
Objectives:	Describe safety and performance of POLYMAILLE® C
Performance primary endpoint:	Primary patency rate at 1 year after surgery using POLYMAILLE® C
Safety primary endpoint:	Mortality rate at 30 days after surgery using POLYMAILLE® C
Performance secondary endpoints:	
 
• Procedural success rate
 
• Primary patency rate at 30 days and 6 months after surgery using POLYMAILLE® C
 
• Primary assisted patency rate at 30 days, 6 months and 1 year after surgery using POLYMAILLE® C
 
• Secondary patency rate at 30 days, 6 months and 1 year after surgery using POLYMAILLE® C
 
• Device failure during procedure or at discharge, at 30 days, 6 months and 1 year after surgery using POLYMAILLE® C
 

PROTOCOL	2020-PMC-01
TITLE:	Safety and Performance of POLYMAILLE® C vascular prosthesis
EFFECTIVE DATE:	15 January 2021

Safety secondary endpoints	
 
• Mortality rate during procedure or at discharge, at 6 months and 1 year after surgery using POLYMAILLE® C
 
• Limb salvage rate at 30 days, 6 months and 1 year after surgery using POLYMAILLE® C
 
• Adverse event during procedure or at discharge, at 30 days, 6 months and 1 year after surgery using POLYMAILLE® C
 

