Exploratory endpoints	
 
- After 1 year until the end of follow-up (5 years) using POLYMAILLE® C: 
 
○ Primary patency
 
○ Primary assisted patency
 
○ Secondary patency
 
○ Device failure
 
○ Mortality
 
○ Limb salvage
 
○ Adverse events
 
 
 
- Identify possible systematic misuse or off-label use of POLYMAILLE® C, with a view to verifying that the intended clinical purpose is correct.
 

Inclusion criteria	Subjects who did receive POLYMAILLE® C at least one year ago for replacement or bypass of pathological arteries.
Exclusion criteria	Patients who have objected to the collect of their data
Duration of the data collect:	6 months from first site operational to collect data until data delivery

---

PROTOCOL	2020-PMC-01
TITLE:	Safety and Performance of POLYMAILLE® C vascular prosthesis
EFFECTIVE DATE:	15 January 2021

---

---

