### **5.3. Subjects**

The participating hospitals will screen all potential subjects and will select those who are appropriate for study inclusion, i.e. subjects implanted with POLYMAILLE® C for at least one year, or with complete data to death. As the study explores real world data, there is no exclusion criteria for subjects and all subjects with POLYMAILLE® C implanted for at least one year and up to 5 years will be included in the study.

All data will be retrieved from medical charts for each patient from time of surgery (considered as index date) until a maximum of 5 years after surgery.

Data from a minimum of 200 from 3 to 8 different sites in France will be evaluated. A minimum of 100 subjects will be evaluated for each main location of surgery (peripheral and abdominal).

Not more than 50% of study total enrolled subjects shall pertain to one unique centre.

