#### **5.3.1. Inclusion criteria**

Patients must meet all the following inclusion criteria in order to be eligible for inclusion in the study:

- Patient has a minimum of 1-year post-operative follow-up data available, or complete data to death

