#### **5.3.2. Exclusion criteria**

Patients who have objected to the collect of their data.

---

PROTOCOL	2020-PMC-01
TITLE:	Safety and Performance of POLYMAILLE® C vascular prosthesis
EFFECTIVE DATE:	15 January 2021

---

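### The entry wordings differ and none expressly admits a patient whose POLYMAILLE C was tried and exchanged during surgery, so procedural success and device failure at surgery can under-count replacements

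*Protocol*

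**What the plan says.** Eligibility is worded in three ways.

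- **Synopsis.** The inclusion criterion is "Subjects who did receive POLYMAILLE® C at least one year ago for replacement or bypass of pathological arteries". The study population entry adds that "data will be collected for all subjects who did receive POLYMAILLE® C".
- **Section 5.3.** Sites select "subjects implanted with POLYMAILLE® C for at least one year, or with complete data to death". The same paragraph then states that "all subjects with POLYMAILLE® C implanted for at least one year and up to 5 years will be included in the study".
- **Section 5.3.1.** The only formal inclusion criterion is "Patient has a minimum of 1-year post-operative follow-up data available, or complete data to death". It does not mention the device.

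The only exclusion, in section 5.3.2, is "Patients who have objected to the collect of their data".

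On the endpoint side, section 7.1 builds procedural success from three parts: "Ability to use with no need for replacement by another device", "Effective vascular flow restoration after procedure" and, for aneurysm cases, exclusion of the aneurysmal portion. Device failure in the same section includes the need to replace the graft wholly or in part, and the table in section 7 schedules it from surgery onward. Section 9.2 plans to collect explant data, including whether the patient is alive.

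**The concern.** An endpoint that asks whether a graft could be used without being exchanged is a statement about attempts. Its failures are the operations that ended with something else in place. If sites list patients by the graft they received or carry, those operations tend not to be listed, and the replacement component is then measured mainly where replacement did not happen.

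The second issue is the asymmetry in section 5.3. It rescues patients who died early, through the clause on complete data to death, but has no matching clause for patients who lived and lost the graft early. Read literally, that removes early explants, which bear on 1-year primary patency, the primary performance endpoint.

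The event is plausible on the protocol's own evidence: the 88-graft survey in section 5.1 reports leakage beneath the bifurcation, torsion and graft bleeding during implantation, all from one centre. A later analysis plan cannot repair the gap, because it cannot recover patients whom sites never listed. With 3 to 8 sites, each could also settle the ambiguity in its own way.

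**Working it through.** There is no figure in the plan to reproduce. Section 8.2 rests the sample size on feasibility, and no procedural success, conversion or explant rate is assumed anywhere. The survey in section 5.1 counted implanted grafts, so it gives no conversion rate either. The check is therefore of the text first, then of scale under stated assumptions.

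**Step 1: who enters.** Consider two living patients with at least one year of follow-up data.

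| Wording | Graft tried and exchanged at the index operation | Graft left in, explanted within the first year |
|---|---|---|
| Synopsis | Undefined: depends on whether a tried graft counts as received | Enters |
| Section 5.3, literal | Left out | Left out |
| Section 5.3, read as time since surgery | Undefined: depends on whether a tried graft counts as implanted | Enters |
| Section 5.3.1 | Follow-up condition met; silent on the device | Enters |
| Section 5.3.2 | Not excluded | Not excluded |

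No row clearly admits the first patient on the strength of an attempted implantation. The second patient is lost on one reading only.

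**Step 2: effect on the replacement component.** Let f be the share of attempts exchanged during surgery and not listed. The documents do not give f; 1% to 3% is an assumption.

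- Failures missed per 200 attempts = 200 × f: 200 × 0.01 = 2; 200 × 0.03 = 6.
- If no other replacements occur, the component reads 100% when the rate over all attempts is 1 − f, that is 99% to 97%.
- Per 200 enrolled, attempts missed = 200 × f/(1 − f): 200 × 0.01/0.99 = 2.0; 200 × 0.03/0.97 = 6.2.

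**Step 3: effect on the composite.** If s is the reported success among listed subjects, success over all attempts is s(1 − f). For an assumed s of 98%: 0.98 × 0.99 = 97.0%; 0.98 × 0.97 = 95.1%.

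**Step 4: comparison with sampling error.** With 0 failures in n, the exact two-sided 95% upper bound on the failure rate is 1 − 0.025^(1/n): 1.8% for n = 200 and 3.6% for n = 100. A study reporting no replacements in 200 would thus give an interval that excludes a true rate of 2% or 3%. At the overall sample size the omission can exceed what the interval conveys; within one surgical location of 100 it would not at these rates.

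**Step 5: 1-year primary patency, literal section 5.3 only.** Assume true patency of 180/200 = 90.0%, and that 1% to 3% of the 200 (2 to 6 living patients, all patency failures) are explanted in the first year and dropped. Then 180/198 = 90.9% and 180/194 = 92.8%, an overstatement of 0.9 to 2.8 percentage points.

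**The case against.** The strongest reply is that one phrase in section 5.3 is being asked to carry too much. Beside the synopsis and the five-year ceiling, being implanted for at least one year reads naturally as time since surgery. The formal criterion in section 5.3.1 asks only for data, objection is the sole exclusion, and section 5 describes an all-comers study. The protocol also plans for replaced grafts: device failure counts replacement at every time point and explant data include whether the patient is living. A patient whose sutured graft was then exchanged can reasonably be said to have received it. Finally, procedural success is secondary in a descriptive study, and section 5.2 places the main evidence gap in long-term and abdominal data.

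Much of this stands. A reader might infer that eligibility requires the graft to have stayed in, that an exchanged patient can never enter, or that procedural success must sit near 100% whatever the device does. The documents do not support this. The retention condition is one reading of one section. A patient with complete data to death can enter. Flow restoration and aneurysm exclusion can fail with the graft in place, and device failure also captures leakage, loss of integrity, occlusion and partial replacement.

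What the reply does not supply is any sentence saying that a tried and exchanged graft counts. A site applying section 5.3 as written would leave out a living patient of that kind. Expecting explants in the data while wording section 5.3 so that it can exclude them is an inconsistency to resolve.

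**Conclusion.** The point holds as a conflict of wording with a consequence for bias. The three entry rules differ, none expressly admits attempted implantations exchanged during the index operation, and a literal section 5.3 excludes them when the patient is alive. Procedural success and device failure at surgery can then under-count replacements, always in the device's favour, and a larger sample does not remove the bias.

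The size rests on an assumed conversion rate of 1% to 3%: about 2 to 6 missed failures per 200 attempts, or 1 to 3 percentage points on the replacement component. The effect on 1-year patency is a conditional illustration. It needs the literal section 5.3 reading together with the assumed explant rate and the assumed 90% patency; on the time-since-surgery reading it disappears. The change is worth making before sites build their lists.

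**What to change.** 1. Reconcile the synopsis and sections 5.3 and 5.3.1 into one rule. Eligibility should run from the date of surgery and cover every subject in whom implantation of POLYMAILLE C was attempted, whether or not the graft was left in place at the end of surgery or later explanted. Keep the existing provision for complete data to death.
2. Have sites identify cases from operative records, so that exchanged grafts can be found.
3. In section 7.1, name all attempts as the denominator for procedural success and for intraoperative device failure.
4. Where a site cannot identify exchanged cases, report its rate as procedural success among implanted subjects, and keep the replacement component for the replacements that are recorded.

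The cost is a protocol wording change, some extra searching of operative records, and possibly a slightly less favourable reported rate.

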## 7.2. Safety endpoints

- Primary safety endpoint is **mortality rate at 30 days** after surgery using POLYMAILLE® C.
- Others study safety endpoints are:
  - **Mortality rate**, *defined as freedom % from death*
  - **Limb salvage rate**, *defined as freedom % from target limb amputation*
  - **Adverse events**, *defined as any documented adverse events, including anticipated (as listed in section 6.2) and non-anticipated adverse events.*

---

PROTOCOL	2020-PMC-01
TITLE:	Safety and Performance of POLYMAILLE® C vascular prosthesis
EFFECTIVE DATE:	15 January 2021

---

## 8. STATISTICAL CONSIDERATIONS

### 8.1. Statistical design, method and analytical procedures

All the patients participating in the study who met the eligibility criteria will be included in the study population.

A descriptive analysis with clinical characteristics of all patients included in the study will be performed at the index date.

Exploratory analyses will be conducted globally and by the 2 sub-populations. Results will be stratified according to 2 main surgical locations:

- Abdominal surgical location:
  - Aorto-aortic and/or aorto-iliac and/or aorto-femoral repair
- Peripheral surgical location:
  - Peripheral artery repair and extra anatomic bypasses

Since no hypotheses will be tested, study objectives will be addressed using descriptive statistics only. Given the real-world nature of the data, the use of multiple imputation methods for missing data would introduce bias as missing data cannot be considered completely at random (MCAR) or at random (MAR). Variables will not be imputed, with the exception of dates in which the exact day is missing: the missing day will be replaced by the middle day of the month.

Continuous variables will be described with number of patients with valid / missing observations, mean and its 95% confidence interval (95%CI), standard deviation (SD), median, 25 and 75 percentiles (P25 and P75, respectively), minimum and maximum. For non-normally distributed continuous variables geometric mean and its 95%CI will be reported too.

For categorical variables counts and percentages per category will be presented. Missing observations (including invalid observations) will be tabulated as a separate category. If the % of missing data does not exceed 10 %, the calculation of proportions will not include the missing/invalid category in the denominators.

P-values will be presented in the summary tables, in association with the descriptive statistics. In addition, 95% confidence intervals (95%CI) will be presented when considered convenient or relevant. Results will be graphically represented when appropriate to make interpretation easier.

The two-sided level of significance will be set at 0.05 for all the statistical tests performed.

Statistical calculations will be carried out by using R software. More details on the statistical analysis will be provided in the Statistical Analysis Plan.

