## 4.2. Intended purpose and patient population

### 4.2.1. Intended clinical purpose

POLYMAILLE®C vascular prostheses are indicated for replacement or bypass of arteries presenting aneurysm or obliterative arterial disease. Their indication is restricted to abdominal and peripheral surgery not crossing the knee flexion crease.

Abdominal vascular surgery includes abdominal aorto-aortic and/or aorto-iliac and/or aorto-femoral vascular repair, i.e. graft implantation with proximal anastomosis to abdominal aorta (supra and/or infra-renal).

Peripheral vascular surgery includes peripheral arteries repair, i.e. graft implantation with no aortic anastomosis, and/or extra-anatomic vascular repair such as axillo-femoral and/or crossover bypass (femoro-femoral and/or ilio-femoral).

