### 4.3. Contra-indications

POLYMAILLE®C vascular prostheses are contraindicated for surgery of the thoracic aorta, coronary bypass, arteriovenous access, extracorporeal circulation and crossing the knee flexion crease.

POLYMAILLE®C vascular prostheses are contraindicated in patients with an immune reaction or hypersensitivity, known or suspected, to collagen of bovine origin.

---

PROTOCOL	2020-PMC-01
TITLE:	Safety and Performance of POLYMAILLE® C vascular prosthesis
EFFECTIVE DATE:	15 January 2021

---

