### **5.2. Rationale for PMCF study**

Available evidence confirms acceptability of performance and side effects related to POLYMAILLE® C; however intended claims on clinical safety and performance are not sufficiently supported with existing clinical evidence, especially for long term assessment and for abdominal surgical locations. In order to keep POLYMAILLE® C in European market, a post-market clinical follow-up (PMCF) study is needed.

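### Section 8.1 names no on-label report of the primary endpoints, so any off-label or contraindicated implants would be pooled into the patency and mortality figures

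*Protocol*

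**What the plan says.** **Population.** Section 8.1: "All the patients participating in the study who met the eligibility criteria will be included in the study population". Results are then shown globally and for two surgical locations, abdominal and peripheral. Label status is not a stratum.

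**Eligibility.** Section 5.3 says that "there is no exclusion criteria for subjects and all subjects with POLYMAILLE® C implanted for at least one year and up to 5 years will" enter the study. The one criterion listed in 5.3.1 is "Patient has a minimum of 1-year post-operative follow-up data available, or complete data to death". Section 5.3.2 removes only patients who object to data collection. The synopsis words inclusion differently: "Subjects who did receive POLYMAILLE® C at least one year ago for replacement or bypass of pathological arteries". Its study-population row says that "data will be collected for all subjects who did receive POLYMAILLE® C".

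**Label.** Section 4.2.1 confines the indication to aneurysmal or obliterative disease, in abdominal or peripheral surgery that stays clear of the knee crease. It explains peripheral repair as "graft implantation with no aortic anastomosis", with extra-anatomic repair added. Under 4.3 the graft is "contraindicated for surgery of the thoracic aorta, coronary bypass, arteriovenous access, extracorporeal circulation and crossing the knee flexion crease". Bovine-collagen hypersensitivity is a further contraindication.

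**Purpose.** Section 5.2 gives the reason for the study: "intended claims on clinical safety and performance are not sufficiently supported with existing clinical evidence". The synopsis and Section 7 also make it an aim to identify misuse or off-label use.

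**The concern.** The study is justified by claims about the intended purpose. The primary figures, as 8.1 sets them up, describe every implant, whatever it was used for. The sponsor expects that some use may be off-label, since it plans to look for it, but identifying such implants does not take them out of the primary rates.

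The location strata do not separate them either. The peripheral stratum in 8.1 carries no knee restriction, so a knee-crossing graft counts among the 100 peripheral subjects and enters their patency. A patient with collagen hypersensitivity could fall in either stratum. Thoracic aortic use fits neither stratum and would reach only the global figure.

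The two inclusion wordings also pull apart. The synopsis version asks for replacement or bypass of diseased arteries; 5.3.1 has no such condition. A site following the synopsis could leave out arteriovenous access or extracorporeal use, which are contraindicated uses that the off-label aim would want to see.

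**Working it through.** **The plan's own figure.** Section 8.2 asks for at least 100 subjects per location: 2 × 100 = 200, as stated. The number rests on feasibility, and no precision or power calculation is given to reproduce.

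**Inputs.** The protocol gives neither an off-label share nor an off-label patency, so both are assumed and varied.

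- q = off-label share: 2% to 20% (assumed).
- Scenario A: 1-year primary patency 90% on-label, 70% off-label (both assumed).
- Scenario B: 95% on-label, the 12-month figure for this graft in the randomised trial summarised in 5.1 (22 above-knee grafts); 50% to 80% off-label (assumed).

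**Formulas.** Pooled rate = (1 − q) × p_on + q × p_off, so the shift is −q × (p_on − p_off). The 95% half-width is 1.96 × √(p(1 − p)/n).

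**Scenario A.**

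- q = 5%: 0.95 × 90 + 0.05 × 70 = 89%, a shift of −1 point.
- q = 10%: 0.90 × 90 + 0.10 × 70 = 88%, −2 points.
- q = 20%: 0.80 × 90 + 0.20 × 70 = 86%, −4 points.
- Half-width at 90%, n=100: 1.96 × √(0.90 × 0.10/100) = 5.9 points. For all 200: 1.96 × √(0.90 × 0.10/200) = 4.2 points.

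Every shift is inside the half-width, although the 20% case comes close to it for the pooled 200.

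**Scenario B** (off-label patency from 80% down to 50%).

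- q = 2%: −0.3 to −0.9 points.
- q = 5%: −0.75 to −2.25 points.
- q = 10%: −1.5 to −4.5 points.
- q = 20%: −3.0 to −9.0 points.
- Half-width at 95%, n=100: 1.96 × √(0.95 × 0.05/100) = 4.27 points.

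Of the cases computed (off-label patency 80%, 65% and 50%), the shift passes the half-width only at q = 10% with 50%, and at q = 20% with 65% or 50%.

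**Mortality.** The same formula applies to 30-day mortality, but the protocol offers no basis for an off-label rate, so no figure is given.

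**Precision of an on-label set.** At 95% patency, removing 5%, 10% or 20% of 100 subjects leaves 95, 90 or 80. The half-width goes from 4.27 to 4.38, 4.50 or 4.78 points.

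**Inclusion wordings side by side.** The synopsis criterion still admits knee-crossing, thoracic aortic and coronary bypass grafts, because these are replacements or bypasses of arteries. What it can shut out is use that is not arterial replacement or bypass, mainly arteriovenous access and extracorporeal circulation. Section 5.3, 5.3.1 and the synopsis population row would keep those in.

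**The case against.** The strongest reply is that nothing here is mis-specified. Section 5 declares an all-comers study, the objective in Section 7 is to describe the device, and both primary endpoints are defined for surgery with the device without reference to the label. No hypothesis or performance goal depends on a labelled-use rate. Section 8.1 defers detail to the statistical analysis plan, where an on-label table could well appear. The data needed for one are largely on the collection list in 9.2.

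Most of this stands. All-comers inclusion is deliberate, and it is the right design for finding misuse. Section 8.1 does not rule out further analysis sets. Two things remain. The protocol names the claim as the reason for the study without naming the set of implants that speaks to it, and that choice is best fixed before results are seen, because a later off-label classification could be coloured by outcome. And the mismatch in inclusion wording lies in the protocol itself; an analysis plan cannot settle it.

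A reader might also infer that the conflicting inclusion texts decide whether misuse can be counted at all. They do not: the commonest arterial forms of misuse one would look for, such as crossing the knee, are admitted under either wording.

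**Conclusion.** The point holds as a gap in reporting. Any off-label or contraindicated implants would be pooled into both primary figures, and the protocol names no on-label report beside them.

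A reader might go further and conclude that the planned figures are biased or are not estimates for labelled use. The documents do not support that. The off-label share is not given and may be zero, in which case the two sets coincide. The manufacturer's survey of 88 implants in 5.1 found no thoracic use, though it reported no indications. Under the assumed 90% and 70%, the effect is 1 to 4 points at shares of 5% to 20%, within sampling error at n=100. It exceeds sampling error only under harsher assumptions, and where off-label patency is worse, pooling lowers the figure and does not flatter the device. For mortality the size cannot be stated.

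The inclusion mismatch is real but narrow, touching mainly arteriovenous and extracorporeal use.

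**What to change.** Keep all-comers collection and the all-comers analysis as planned. Then:

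1. Add to 8.1 that 1-year primary patency and 30-day mortality are also reported, overall and by location, for implants within the 4.2.1 indication and outside the 4.3 contraindications.
2. Derive the on-label flag from the indication, surgery location, native vessel and anastomosis items already in 9.2. Set it without knowledge of outcome.
3. State the number of off-label implants, and the number on-label in each location.
4. Reconcile the synopsis inclusion criterion with 5.3.1 and with the synopsis population row, so that arteriovenous and other non-arterial uses are not screened out of the off-label objective.

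The minimum of 100 per location should not have to be met on-label. That would mean enrolling more subjects when 8.2 set the number by what the hospitals can supply; reporting the on-label number is enough.

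The cost is one derived flag and an extra set of columns. The on-label set is somewhat smaller: at 95% patency the half-width goes from 4.27 to 4.50 points if 10% are off-label. The 9.2 items are collected only when available, so some implants may be unclassifiable and should be counted as such. Bovine-collagen hypersensitivity is not named in 9.2 and can be flagged only if it is recorded.

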### 9.4. Missing data

Some endpoints can be missing for some subjects. Endpoints proportions will be calculated on the number of non-missing observations. No imputation method is planned.

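### The reason section 8.1 gives for rejecting imputation applies at least as strongly to the observed-case proportions used instead, no bounding analysis is stated, and sections 8.1 and 9.4 give conflicting denominators.

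*Protocol*

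**What the plan says.** The protocol names its primary performance measure in section 7.1: "Primary performance endpoint is primary patency rate at 1 year after surgery using POLYMAILLE® C". It deals with missing values in two places.

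- **Section 8.1** argues that "multiple imputation methods for missing data would introduce bias as missing data cannot be considered completely at random (MCAR) or at random (MAR", and continues: "Variables will not be imputed, with the exception of dates in which the exact day is missing". For categorical variables it adds "Missing observations (including invalid observations) will be tabulated as a separate category", and then "If the % of missing data does not exceed 10 %, the calculation of proportions will not include the missing/invalid category in the denominators". It states no rule for more than 10% missing; the implication is that missing values then stay in the denominator.
- **Section 9.4** accepts that "Some endpoints can be missing for some subjects" and sets a rule without any threshold: "Endpoints proportions will be calculated on the number of non-missing observations. No imputation method is planned".

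Section 8.1 also says that the study tests no hypotheses and is descriptive, and refers further statistical detail to the SAP, which is not at hand.

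**The concern.** An unadjusted proportion among observed subjects estimates the rate in all included subjects only if patent and failed grafts are equally likely to have a recorded status. In practice that means missingness unrelated to outcome, which is an MCAR-like condition. Standard multiple imputation needs only MAR, that is, missingness unrelated to outcome once the recorded covariates are taken into account. Section 8.1 denies both conditions, uses the denial to exclude imputation, and keeps an estimate that in general relies on the more demanding of the two.

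One-year patency is read from charts. Section 9.2 acknowledges that follow-up practice differs between sites and that data are taken as available. Whether a graft is assessed may depend on symptoms, which would over-represent failures, or on the patient staying well enough to attend, which would over-represent successes. The rate would be reported as a plain estimate, and a confidence interval around it reflects sampling error only.

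The two sections also disagree about the denominator. Above 10% missing, the headline rate depends on which section the analyst follows.

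**Working it through.** The protocol gives no expected missing fraction, precision target or bias figure, so there is no stated figure to reproduce.

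**Inputs.** From the protocol: at least 100 subjects per surgical location (section 8.2); the 10% threshold (section 8.1); 95% primary patency at 12 months in the polyester arm (n = 22) of the earlier randomised trial (section 5.1), used only as an illustration. Assumed: observed patency of 90% as a second illustration, missing fractions of 10%, 11% and 20%, and the patency and missingness values in steps 1 and 2.

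**1. Does the observed-case rate need more than MAR?** Take two equal strata with patency 95% and 75%, and with 5% and 30% missing, depending on stratum only (MAR).
- True rate: 0.5 × 0.95 + 0.5 × 0.75 = 85.0%.
- Observed-case rate: (0.5 × 0.95 × 0.95 + 0.5 × 0.70 × 0.75) / (0.5 × 0.95 + 0.5 × 0.70) = 0.71375 / 0.825 = 86.5%.
- A method that uses the strata recovers 85.0%.

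So the observed-case rate can be biased where a MAR-based method is not.

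**2. Which way does bias run if missingness depends on outcome?** With true patency π, and missing fractions m1 in patent and m0 in failed grafts, the observed-case rate is π(1 − m1) / [π(1 − m1) + (1 − π)(1 − m0)]. For π = 80%:
- m1 = 10%, m0 = 30%: 0.72 / 0.86 = 83.7%, an overstatement of 3.7 points.
- m1 = 30%, m0 = 10%: 0.56 / 0.74 = 75.7%, an understatement of 4.3 points.
- m1 = m0 = 20%: 0.64 / 0.80 = 80.0%, no bias.

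**3. How far could the rate move?** With observed rate p and missing fraction f, the lower limit (all missing failed) is p(1 − f) and the upper limit (all missing patent) is p(1 − f) + f.

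| p | f | Lower | Upper |
|---|---|---|---|
| 90% | 10% | 81% | 91% |
| 90% | 20% | 72% | 92% |
| 95% | 10% | 85.5% | 95.5% |
| 95% | 20% | 76% | 96% |

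At p = 95% and f = 10%, the overstatement could reach 95 − 85.5 = 9.5 points. The Wald 95% half-width at 95% with n = 100 is 1.96 × √(0.95 × 0.05 / 100) = 4.3 points, or 4.5 points on the 90 observed. The interval would not convey the larger uncertainty.

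**4. Do the denominator rules agree?** Up to 10% missing, yes. At f = 11% and p = 95%, section 9.4 gives 95%. The rule implied by 8.1 gives 0.95 × 0.89 = 84.55%, about 84.6%. The gap is about 10 points. The 8.1 figure equals the all-failed limit, so crossing the threshold would switch the estimate from observed-case to worst-case.

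**The case against.** Several points on the other side are sound.

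- **The sentence on imputation is defensible in itself.** Standard MAR-based imputation can be biased when missingness depends on the unseen outcome. That stands. The fault is that the argument stops there, as if avoiding imputation avoided the bias.
- **A reader might infer that the primary rate is biased without limit.** The documents do not support that. Denying MCAR and MAR removes the guarantee of an unbiased rate but fixes neither size nor direction, as step 2 shows. Missing counts are to be tabulated, so a reader can derive the limits, and with no more than 10% missing the error cannot exceed 10 points.
- **A reader might also infer that observed cases are the only estimate planned.** Section 8.1 drops missing values only up to 10%; the unconditional rule is in 9.4.
- **Eligibility reduces missingness.** Section 5.3.1 requires one year of follow-up data or complete data to death, so 30-day vital status should be nearly complete and large gaps at one year may be unlikely. But follow-up data in a chart are not necessarily a patency assessment, and 9.4 itself expects missing endpoints.
- **Sensitivity analyses often belong in the SAP.** True, and their absence from a protocol would not alone be a finding. The SAP may contain them. It would still inherit the incomplete rationale and two conflicting denominators, both fixed here.
- **Section 9.4 could be read as the specific rule that overrides 8.1 for endpoints.** That is possible, but patency status is a categorical variable and the protocol does not say which section prevails.

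**Conclusion.** The point holds in limited form. The stated reason for rejecting imputation applies at least as strongly to the observed-case proportion, so on the plan's own premise the 1-year primary patency rate is not protected from bias in either direction, and the protocol states no bounding analysis. Separately, 8.1 and 9.4 conflict above 10% missing, by about 10 points in the illustration at 11%.

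The possible size depends on the missing fraction, which the documents do not give. The ranges above rest on assumed observed rates and are limits, not predictions. The 84.6% also rests on reading 8.1 as keeping missing values in the denominator above 10%, which it implies but does not state. Nothing here shows that the reported rate will be wrong, or in which direction.

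**What to change.** 1. In section 8.1, keep the caution about MAR-based imputation and add that the observed-case rate is also open to bias under the missingness the protocol asserts.
2. Reconcile 8.1 and 9.4 into one denominator rule for the endpoints, applied at every level of missingness.
3. Beside the observed-case 1-year primary patency rate, globally and for the abdominal and peripheral locations, report the number missing and the two limits: all missing counted as failure and all counted as success. Do the same for 30-day mortality if any vital status is unknown. Quote the range with the conclusion.

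This takes short edits to two sections and one extra table, with no new data. The downside is a wider and less favourable stated range.
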